### 21.2. Relationship to Study Device(s)

The investigator must assess the relationship of the AE to the study device as related or unrelated. See criteria in Table 21.2-1:

**Table 21.2-1: Criteria for Assessing Relationship of Study Device to Adverse Event**

Classification	Description
Unrelated	The adverse event is determined to be due to a concurrent illness or effect of another device/drug and is not related to the investigational product.
Related	
 
The adverse event is determined to be potentially related to the investigational product, and an alternative etiology is equally or less likely compared to the potential relationship to investigational product, or
 
There is a strong relationship to investigational product, or recurs on re-challenge, and another etiology is unlikely, or
 
There is no other reasonable medical explanation for the event.
 

### 21.3. Relationship to Study Procedure

The investigator must assess the relationship of the AE to the study procedure as unrelated, possibly related, or probably related. See criteria in Table 21.2-1:

**Table 21.3-2: Criteria for Assessing Relationship to Study Procedure**

Classification	Description
Unrelated	
 
No evidence that the timing of the adverse event has a relationship to the procedure performed.
 

Possibly Related	
 
The adverse event has a timely relationship to procedure performed. However, a potential alternative etiology may be responsible for the adverse event.
 

Probably Related	
 
The adverse event has a timely relationship to the study procedure performed and the causative relationship can be clearly established. No potential alternative etiology is apparent.
 

**21.4. Investigator Reporting Requirements**

The communication requirements for reporting to BSC are as shown in Table 21.4-1.

**Table 21.4-1: Investigator Reporting Requirements**

[figure not shown]
Event Classification	Communication Method	Communication Timeline

Adverse device Effects and Serious Adverse Device Effects.
 
Events assessed for reporting shall include but are not limited to:
 
 
• Mesh exposure in the vagina
 
• Mesh erosion into the bladder
 
	
Complete AE CRF page with all available new and updated information
 
If requested by Boston Scientific provide all relevant source documentation (unidentified) for the reported event
	
 
• Within 2 business days of first becoming aware of the event or as per local/regional regulations.
 
• Reporting required through the end of the study
 
• When documentation is available
 

Adverse Events related to the study procedure for both surgical groups.
 
Events assessed for reporting shall include but are not limited to:
 
 
• Organ perforation
 
• Bleeding (including hemorrhage and hematoma)
 
• Pelvic pain
 
• Infection
 
• De novo dyspareunia
 
• Urinary retention
 
• Recurrent incontinence
 
• Other urinary problems
 
• Neuromuscular problems
 
• Revision/re-surgery
 
	
Complete the AE CRF page, which contains such information as onset date of the AE, treatment provided if any, resolution, assessment of seriousness, and relationship to study device.
	
 
• Within 2 business days of first becoming aware of the event or as per local/regional regulations.
 
• Reporting required through end of subject participation
 

Device Deficiencies (including but not limited to failures, malfunctions, and product nonconformities)
 
Note: Any Investigational Device Deficiency that might have led to a serious adverse event if a) suitable action had
	
Complete CRF with all available new and updated information
	
 
• Within 1 business day of first becoming aware of the event and as per local/regional regulations
 
• Reporting required through the end of the study
 

**Table 21.4-1: Investigator Reporting Requirements**

Event Classification	Communication Method	Communication Timeline
not been taken or b) intervention had not been made or c) if circumstances had been less fortunate is considered a reportable event.		

[figure not shown]
Abbreviations: AE=adverse event; CRF=case report form

**21.6. Reporting to Regulatory Authorities / IRBs / ECs / Investigators**

BSC is responsible for reporting adverse event information to all participating investigators and regulatory authorities, as applicable.

The Principal Investigator is responsible for informing the IRB/EC, and regulatory authorities of an SAE at his/her clinical site as required by local/regional regulations.

## 23. Suspension or Termination

### 23.1 *Premature Termination of the Study*

Boston Scientific Corporation reserves the right to terminate the study at any stage but intends to exercise this right only for valid scientific or administrative reasons and reasons related to protection of subjects. Investigators, associated IRBs/ECs, and regulatory authorities, as applicable, will be notified in writing in the event of study termination.

#### 23.1.1 **Criteria for Premature Termination of the Study**

Possible reasons for premature study termination include, but are not limited to, the following.

- The occurrence of safety events that present a significant or unreasonable risk to subjects enrolled in the study
- An enrollment rate far below expectation that prejudices the conclusion of the study
- A decision on the part of Boston Scientific to suspend or discontinue development of the device

### 23.2 *Termination of Study Participation by the Investigator or Withdrawal of IRB/ EC Approval*

Any investigator, or IRB/ EC in the Solyx Study may discontinue participation in the study or withdrawal approval of the study, respectively, with suitable written notice to Boston Scientific. Investigators, associated IRBs/ECs, and regulatory authorities, as applicable, will be notified in writing in the event of these occurrences.

### 23.3 *Requirements for Documentation and Subject Follow-up*

In the event of premature study termination a written statement as to why the premature termination has occurred will be provided to all participating centers by Boston Scientific. The IRB/EC and regulatory authorities, as applicable, will be notified. Detailed information on how enrolled subjects will be managed thereafter will be provided.

In the event an IRB or EC terminates participation in the study, participating investigators, associated IRBs/ECs, and regulatory authorities, as applicable, will be notified in writing. Detailed information on how enrolled subjects will be managed thereafter will be provided by Boston Scientific.

In the event an investigator terminates participation in the study, study responsibility will be transferred to a co-investigator, if possible. In the event there are no opportunities to transfer

investigator responsibility; detailed information on how enrolled subjects will be managed thereafter will be provided by Boston Scientific.

**23.4 Criteria for Suspending/Terminating a Study Center**

Boston Scientific Corporation reserves the right to stop the inclusion of subjects at a study center at any time after the study initiation visit if no subjects have been enrolled for a period beyond 12 months after center initiation, or if the center has multiple or severe protocol violations/noncompliance without justification and/or fails to follow remedial actions.

In the event of termination of investigator participation, all testing equipment, as applicable, will be returned to BSC unless this action would jeopardize the rights, safety or well-being of the subjects. The IRB/EC and regulatory authorities, as applicable, should be notified. All subjects enrolled in the study at the center will continue to be followed per protocol requirements. The Principal Investigator at the center must make provision for these follow-up visits unless BSC notifies the investigational center otherwise.

[figure not shown]

- [Redacted]
- [Redacted]
- [Redacted]
- [Redacted]
- [Redacted]
- [Redacted]
- [Redacted]
- [Redacted]
- [Redacted]
- [Redacted]
- [Redacted]
- [Redacted]
- [Redacted]
- [Redacted]
- [Redacted]
- [Redacted]

- [Redacted]
- [Redacted]
- [Redacted]
- [Redacted]
- [Redacted]
- [Redacted]
- [Redacted]
- [Redacted]
- [Redacted]
- [Redacted]
- [Redacted]
- [Redacted]
- [Redacted]
- [Redacted]
- [Redacted]

■ [Redacted]

■ [Redacted]

■ [Redacted]

## 26. Abbreviations and Definitions

### 26.1. Abbreviations

Abbreviations are shown in Table 26.1-1.

**Table 26.1-1: Abbreviations**

Abbreviation/Acronym	Term
Refer to Manual of Operations	

### 26.2. Definitions

Terms are defined in Table 26.2-1.

**Table 26.2-1: Definitions**

Term	Definition
Refer to Manual of Operations	

Abbreviations are defined in Table 26.1-1.

[Redacted]

[Redacted]

[Redacted]

1 PROTOCOL SUMMARY

Objective	The purpose of this study is to compare a single incision midurethral sling to a standard outside-in transobturator sling for the treatment of female stress urinary incontinence.
Test Device	Solyx™ Single Incision Sling System
Control Device	Obtryx™ II Sling System (outside-in transobturator sling)
Study Design	Prospective, non-randomized, parallel cohort, multi-center study
Planned Number of Subjects	Approximately 280 subjects (140 in each study arm) are planned
Planned Number of Centers	Up to 30 study centers
Primary Endpoint	Treatment success at 36 months defined as negative cough stress test with protocol required bladder fill procedure and subject self-reported improvement in their condition as compared to baseline on the Patient Global Impression of Improvement (PGI-I).
[REDACTED]	[REDACTED]
Method of Assigning Subjects to Treatment	Physicians and study centers will be selected based on their device experience and will be device-specific centers (i.e. Solyx™ or Obtryx II™ subjects only).
Follow-up Schedule	Study follow-up duration is for 3 years from primary study procedure: 
 • Screening/Enrollment Visit • Pre-operative/Baseline Visit

	
• Surgery and Discharge• Week 2 Visit• Week 6 Visit• Month 6 Visit• Month 12 Visit• Month 18 Visit• Month 24 Visit• Month 36 Visit (End of study)
Key Inclusion Criteria	
1. Female \geq 18 years of age2. Willing and able to comply with the study procedures and provide written informed consent to participate in the study (subject or legal representative)3. Diagnosed with predominant SUI confirmed by positive cough stress test during the protocol required bladder fill procedure (see manual of operations)4. Confirmed SUI is greater than urge incontinence with MESA5. Cystometric capacity \geq 300 cc6. Post-void residual (PVR) of \leq 150 cc7. Medically approved for general, regional or monitored anesthesia


Key Exclusion Criteria
	
 1. Subjects who are pregnant, lactating, or planning future pregnancies 2. Subjects with a chief complaint of overactive bladder 3. Subjects with a pattern of recurrent urinary tract infections, defined as ≥ 2 culture-proven urinary tract infections during a 6-month period prior to surgery or ≥ 3 in a 12-month period 4. Subjects with previous surgical procedures for SUI including bulking, urethral sling, bone anchor, Burch procedure, pubo-vaginal sling, and MMK procedure. Previous surgical procedures for SUI does not include Kelly plication, Botox, anterior repair, or Inter-Stim. 5. Subjects with prior pelvic organ prolapse surgery who experienced mesh complications 6. Subjects with previous radiation therapy to the pelvis 7. Subjects with known or suspected hypersensitivity to polypropylene mesh 8. Subjects with any of the following confounding conditions: 
 a. Neurogenic bladder b. Urethral stricture and bladder neck contracture c. Bladder stones or tumors d. Urinary tract fistula or diverticula e. Pathology which would compromise implant placement including subjects currently taking anticoagulation therapy f. Pathology that would limit blood supply or infections that would compromise healing including chemotherapy, systemic steroids and systemic immunosuppressants 9. Subjects with diabetes and an A1c $\geq 7\%$ 10. Non-English speaking subjects 11. Subjects who have participated in an investigational study (medical device or drug) within 30 days of study entry that may impact analysis of this device or have previously participated in the current study

Primary Statistical Hypothesis
	
The efficacy of the single incision sling treatment is non-inferior to that of the standard outside-in transobturator sling treatment.

2 INTRODUCTION

This is a post-market surveillance study required by the Food and Drug Administration per Section 522 of the Federal Food, Drug, and Cosmetic Act. [REDACTED]

3 ENDPOINT ANALYSIS

3.1 Primary Endpoint

The primary endpoint of the study is treatment success at 36 months defined as a negative cough stress test and a subject-reported improvement in their condition through the Patient Global Impression of Improvement (PGI-I). Improvement per the PGI-I is defined as a response of “A little better”, “Much better”, or “Very much better”. A negative cough stress test is defined as an answer of “No” to the item “Direct observation of urine loss with cough provocation”.

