## 2. Protocol Synopsis

Postmarket Solyx™ Study PS120093: A Prospective, Non-Randomized, Parallel Cohort, Multi-center Study of the Solyx™ Single Incision Sling System vs. the Obtryx™ II Sling System for the Treatment of Women with Stress Urinary Incontinence	
Objective(s)	The purpose of this study is to compare a single incision midurethral sling to a standard outside-in transobturator sling for the treatment of female stress urinary incontinence. It is hypothesized that the single incision sling will be non-inferior to the transobturator device in safety and effectiveness.
Test Device	Solyx™ Single Incision Sling System
Control Device	Standard outside-in transobturator sling (i.e. Obtryx™ II Sling System)
Study Design	
Prospective, non-randomized, parallel cohort, multi-center study
 
All study procedures will be standardized for uniformity. Physicians will have to document a minimum of ~10 procedures per device prior to participation in order to document competency and experience. Surgeons in the Obtryx cohort must complete a minimum of 5 Obtryx II cases to meet their case prerequisite obligation. [REDACTED]
 
Concomitant procedures including pelvic floor repair can occur, per physician discretion. All concomitant procedures performed will be recorded.
 
Subjects who undergo a medical intervention (surgical or non-surgical) to treat recurrence, persistence of SUI, or a mesh complication will be followed to 36 months from the initial study procedure.

Planned Number of Subjects	Assuming 20% lost to follow-up at 36 months, approximately 280 subjects (140 in each study arm) are planned
Planned Number of Centers / Countries	Up to 30 study centers

**Postmarket Solyx™ Study PS120093: A Prospective, Non-Randomized, Parallel Cohort, Multi-center Study of the Solyx™ Single Incision Sling System vs. the Obtryx™ II Sling System for the Treatment of Women with Stress Urinary Incontinence**

Primary Endpoint	The primary endpoint is an assessment of improvement in stress urinary incontinence at 36 months as compared to Baseline, by a composite of objective and subjective measures: negative cough stress test with protocol required bladder fill procedure and a subject self-reported improvement in their condition, through the Patient Global Impression of Improvement (PGI-I).
[REDACTED]	[REDACTED]

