### 7. Endpoints

#### Primary Endpoint

The primary endpoint of the study is an assessment of improvement in stress urinary incontinence at 36 months as compared to Baseline by a composite of objective and subject measures: negative cough stress test with protocol required bladder fill procedure (see manual of operations) and a subject self-reported improvement in their condition through the Patient Global Impression of Improvement (PGI-I).

[REDACTED]

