### **11.6. Re-Intervention**

It is the intention of this study to demonstrate an improvement in stress urinary incontinence through clinical effectiveness of a single incision sling. However, it is recognized that during the course of the study, there is a possibility subjects may require a re-intervention for events including but not limited to failed sling repair, persistence of SUI symptoms, or a mesh-related complication. A re-intervention may include surgical or non-surgical treatments (medical). For the purpose of this study surgical interventions shall be classified as “re-surgery” and non-surgical interventions shall be classified as “re-interventions”.

Non-surgical interventions (re-interventions) are defined as office-based procedures and do not involve an operating room procedure. Examples of non-surgical interventions may include but are not limited to an office visit to trim exposed mesh in the vagina or physical therapy to treat procedural complications or persistent SUI symptoms. Data on non-surgical interventions will be captured in the CRFs. Subjects will continue to be followed per the regular study visit schedule.

Surgical interventions (re-surgery) are surgical operations or procedures performed to correct recurring SUI symptoms or a mesh-related complication. These surgical events typically may occur on an outpatient basis yet can require admission to a hospital. Surgical events may include a re-operation to remove mesh material or to loosen the sling as well as a bulking agent application to treat recurrence. The decision to perform a re-surgery will be per physician and subject discretion and all re-surgery data will be captured in the Case Report Forms. Subjects undergoing re-surgery to treat recurrence or persistence of SUI symptoms are considered treatment failures.

Subjects undergoing a re-surgery will be followed to 36 months post their initial study procedure as indicated in [REDACTED]. The subject should return to the clinic for the next regular study visit as per the adjusted schedule. If the subject elects to not undergo re-surgery, then the subject will be followed to the Month 36 visit unless the subject chooses to withdraw consent from the study. No subject will be followed for more than 36 months beyond their initial study procedure.

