5.2 Justification of Pooling

In this study, the treatment difference will be estimated by pooling across propensity score strata. An analysis of the poolability will be made using logistic regression for the primary endpoint with fixed effects for treatment arm, propensity score stratum, and their interaction. The interaction will be evaluated to assess the extent of heterogeneity in the treatment difference across strata, and hence whether pooling the within-stratum treatment differences is justified. In addition, within each treatment arm, a chi-squared test will be applied to assess whether the distribution of the primary endpoint varies across the study centers. The above methods will be used in lieu of performing the protocol-specified logistic regression with effects for treatment arm and study center, since the treatment arm and center are confounded.

[REDACTED]

[REDACTED]

[REDACTED]

[REDACTED]

[REDACTED]

[REDACTED]

- [REDACTED]

[REDACTED]

[REDACTED]

[REDACTED]

[REDACTED]

[REDACTED]

[REDACTED]

[Redacted]

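### The visible primary-endpoint definition (SAP 3.1 and the protocol's own endpoint text) does not carry the rule in protocol 11.6 that re-surgery for recurrent or persistent SUI is a treatment failure

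*SAP*

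**What the plan says.** **Endpoint definition.** SAP 3.1 gives "treatment success at 36 months defined as a negative cough stress test and a subject-reported improvement in their condition through the Patient Global Impression", meaning the PGI-I. It then specifies which case report form answer makes the cough test negative and which three PGI-I responses count as improvement. SAP section 1 has the same two components, beginning "Treatment success at 36 months defined as negative cough stress test with protocol required bladder fill procedure". The protocol synopsis describes "improvement in stress urinary incontinence at 36 months as compared to Baseline, by a composite of objective and subjective measures", and protocol section 7 an "assessment of improvement in stress urinary incontinence at 36 months as compared to Baseline by a composite of objective and subject measures"; both then name the cough test and the PGI-I. None of these places mentions re-surgery or points to section 11.6.

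**Re-surgery.** Protocol 11.6 defines the term broadly: "Surgical interventions (re-surgery) are surgical operations or procedures performed to correct recurring SUI symptoms or a mesh-related complication". It attaches an outcome to only part of that group: "Subjects undergoing re-surgery to treat recurrence or persistence of SUI symptoms are considered treatment failures". It also says "Subjects undergoing a re-surgery will be followed to 36 months post their initial study procedure", and that re-surgery data are recorded on the Case Report Forms.

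**Missing Month 36 data.** Protocol 10.2 keeps withdrawn subjects in the ITT analysis. The visible default in SAP 4.6 and protocol 12.2.1 is an available-case analysis unless otherwise specified.

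**Decision rule.** SAP 3.1.3 requires the two-sided 90% confidence interval for Solyx minus Obtryx II to lie wholly above -15%.

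**The concern.** Because women who have re-surgery stay in follow-up, both endpoint components can be observed after a second operation. A woman whose SUI recurred, who was re-operated, and who is dry and improved at Month 36 meets the SAP 3.1 definition of success. Protocol 11.6 calls her a treatment failure. An analyst who programs the primary endpoint from SAP 3.1 as written would credit the sling with the result of a second procedure.

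This raises the success rate in each arm by that arm's re-surgery rate times the share of its re-operated women who pass both components. If that product differs between arms, the treatment difference moves, and the non-inferiority conclusion can move with it.

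There is a related gap. A woman re-operated for SUI who has no Month 36 visit would drop out under the available-case default, although her status under section 11.6 is already settled.

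**Working it through.** **Step 1. The texts side by side, for a woman re-operated for SUI**

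| Month 36 status | SAP 3.1 (also SAP 1, protocol 2 and 7) | Protocol 11.6 |
|---|---|---|
| Cough test negative, PGI-I improved | Success | Failure |
| Cough test positive or PGI-I not improved | Failure | Failure |
| No Month 36 visit | Not counted under the visible available-case default | Failure |

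The rules disagree in the first and third rows. Steps 2 to 4 size the first.

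**Step 2. Inputs**

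- From the documents: 140 per arm with 20% loss (protocol synopsis), so 140 x 0.80 = 112 evaluable per arm, and 112/0.80 = 140 returns the stated figure. Margin 15 points and two-sided 90% interval (SAP 3.1.3), which is a one-sided 5% test. The full sample size cannot be reproduced, because the assumed success rates and power are not visible.
- Assumed, because the documents give no figures: the re-surgery rates for SUI, r; the share s of re-operated women who pass both components; and true success rates, with re-surgery for SUI counted as failure, of 70% Solyx and 85% control. That difference is exactly -15 points, so any claim of non-inferiority is false.

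**Step 3. Formulas**

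Observed success in an arm = true success + r x s.

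Shift in the difference = (r x s for Solyx) - (r x s for control). It is zero only if the two products are equal.

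Probability of declaring non-inferiority = Phi((d + 0.15)/SE - 1.645), where d is the observed difference and SE is the unpooled standard error with 112 per arm. Propensity stratification is ignored.

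Worked case, re-surgery 8% Solyx vs 3% control, s = 0.8 in both arms:

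- Solyx: 0.70 + 0.08 x 0.8 = 0.764. Control: 0.85 + 0.03 x 0.8 = 0.874. d = -0.110.
- SE = sqrt(0.764 x 0.236/112 + 0.874 x 0.126/112) = 0.0509.
- Phi(0.040/0.0509 - 1.645) = 19.5%.

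**Step 4. Results (nominal 5.0%), same s in both arms**

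| Re-surgery, Solyx vs control | s = 0.2 | s = 0.5 | s = 0.8 |
|---|---|---|---|
| 5% vs 5% | 5.0% | 5.0% | 5.0% |
| 5% vs 3% | 5.8% | 7.3% | 9.1% |
| 8% vs 3% | 7.2% | 12.1% | 19.5% |
| 3% vs 8% | 3.4% | 1.7% | 0.7% |

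Equal re-surgery rates are not enough to remove the bias. At 5% in both arms, with s = 0.8 for Solyx and 0.5 for control, the shift is 0.05 x 0.8 - 0.05 x 0.5 = 1.5 points and the error is 8.8%.

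In the other direction the cost is power. If both slings truly succeed in 85%, power is 93.3% with re-surgery for SUI scored as failure. At 3% vs 8% re-surgery under the literal SAP definition, it is 88.7% (s = 0.5) or 85.0% (s = 0.8).

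**The case against.** **The rule may exist where we cannot see it.** Text is redacted after the endpoint in protocol section 7, after the primary-endpoint row in SAP section 1, after SAP 3.1.3, and within SAP 4.6, where the available-case default itself allows for exceptions. Protocol 26.2 sends definitions to the Manual of Operations. This stands, and it makes the point conditional. It does not remove the visible disagreement: the SAP 3.1 definition shows no redaction and goes down to form-item wording, yet has no re-surgery clause or pointer.

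**Section 11.6 does not name the composite.** Also true. SAP 4.6 gives censoring rules for time-to-event analyses that are not visible, and the failure status could serve one of those. But SAP 3.1.1 tests the proportions with treatment success, and treatment failure is its plain opposite. The link is the natural reading, not an express statement.

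**The protocol already governs.** Where the SAP visibly departs from the protocol it says so; on pooling it states "The above methods will be used in lieu of performing the protocol-specified logistic regression with effects for treatment arm and study center". It announces no departure here, so section 11.6 appears to remain in force, and harm needs someone to program from SAP 3.1 alone. That is fair, but the protocol's own endpoint sections omit the rule too, so checking them would not expose the slip.

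**The error rates are hypothetical.** They are. The upper figures need a 5-point gap in re-surgery rates and a high pass share, and nothing in the documents supports either. At a 20% share, 8% vs 3% gives only 7.2%.

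**Conclusion.** On the visible text, two stated rules classify the same woman in opposite ways on the primary endpoint. The gap begins inside the protocol, between sections 2 and 7 on one side and 11.6 on the other, and SAP sections 1 and 3.1 carry it forward. It deserves repair before analysis, because a literal reading of SAP 3.1 gives a primary result that section 11.6 contradicts.

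The size and direction are unknown. Under the assumptions above, false non-inferiority ranges from 0.7% to 19.5% over the re-surgery rates and shares shown, and stays at 5.0% when the products of re-surgery rate and pass share are equal in the two arms.

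A reader might go further in three ways that the documents do not support:

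- That the SAP dropped a protocol rule, or that the final analysis will count these women as successes. The SAP repeats the protocol's own two-component endpoint, and unseen text may already settle the scoring.
- That the omission favours Solyx. No re-surgery rates are given for either arm, and the effect can run either way.
- That all re-surgery or any re-intervention is a failure. Section 11.6 gives that status only to re-surgery for recurrent or persistent SUI.

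**What to change.** Reconcile protocol 11.6 with the endpoint text in protocol sections 2 and 7 and SAP sections 1 and 3.1. First check whether the redacted text or the Manual of Operations already does this. If not, add one sentence or cross-reference to SAP 3.1 and to the protocol endpoint text, applying section 11.6 to the primary composite: re-surgery for recurrent or persistent SUI before Month 36 is scored as failure whatever the Month 36 cough test and PGI-I show. State that the same holds when such a woman has no Month 36 visit, so that the available-case default does not remove her. Leave the status of re-surgery for mesh complications and of non-surgical re-intervention as the protocol has it.

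The cost is a sentence in each document. Section 11.6 already has re-surgery data recorded on the Case Report Forms, so no new data are needed, and the planned sample size does not change. The downside is slightly lower reported success rates.
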